## **1 INTRODUCTION**

### **1.1 Background**

Rabies is an acute lethal zoonotic disease transmitted from animals to humans. Rabies is known to be present in more than 150 countries and territories and on every continent except Antarctica, and all mammals are believed to be susceptible to infection with the virus. In the US, multiple rabies virus variants are maintained in wild mammalian reservoir populations such as raccoons, skunks, foxes, and bats. Infected domestic and wild animals spread rabies to humans via saliva or scratches (Gompf, 2014). Although the US has been declared free of canine rabies virus variant transmission, in developing countries, the primary route of transmission to humans is via the bite of a rabid dog (Manning et al. 2008). There are currently no known effective rabies antiviral drugs.

Once the clinical signs of rabies manifest, the mortality rate approaches 100%. Therefore, post-exposure prophylaxis against rabies infection is of critical importance. Rabies vaccination alone is used for preexposure prophylaxis (Fishbein, 1989). Studies on the development of rabies virus neutralizing activity through immunization indicate that on Day 7 post vaccination most individuals lack adequate rabies virus neutralizing activity while by Day 14 after immunization virtually all individuals vaccinated with a modern vaccine have adequate rabies neutralizing activity (Grandien 1976, Vodopija 1988a)

The rabies mortality from rabid wolf attacks in Iran in 1955 was 1/24 (4.2%) when both vaccination and rabies antisera were used prior to disease manifestations versus 3/5 (60%) when vaccine alone was employed (Baltazard 1955). A study by the same investigator from 1974 found that a rabies vaccine from human diploid cells combined with mule derived anti-rabies antiserum yielded 0% rabies mortality in 44 bitten individuals without disease manifestations even with delays of up to 14 days (Bahmanyar 1976). Delays of up to 4 days in the initiation of rabies immune globulin after anti-rabies vaccination have demonstrated no inhibition of the RVNA activity in blood (Khawplod 1996). Since those experiences post-exposure prophylaxis through the combined administration of a rabies vaccines and rabies immune globulin (RIG) is the standard of care.

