## **1.6 Rationale for Study**

Monoclonal antibodies (mAbs) offer the advantages of batch-to-batch consistency and large-scale production, and may therefore provide a solution to the current global shortage of RIG. However, as mentioned, there are several strains of the rabies virus that predominate in various regions of the US and the world; their prevalence is tracked by the Centers for Disease Control and Prevention (CDC) and the World Health Organization (WHO). A single target epitope may not be present on all strains of the rabies virus. As a result, it is of critical importance for the antibody product to account for the genetic variability of the rabies viruses and offer effective broad spectrum neutralization activities. Accordingly, administration of a mixture of mAbs with complementary specificity and functionality would be preferable to administration of a single mAb.

Consensus definitions of adequate rabies virus neutralizing antibody reference values have been developed to define an appropriate, intact adaptive host response to vaccination: RVNA of 0.5 international units (IU) per milliliter (mL) or complete virus neutralization at a 1:5 serum dilution by RFFIT (Centers for Disease Control and Prevention 1999). The goal of RIG and SYN023 is to rapidly establish protective rabies virus neutralizing levels in the rabies exposed person. RVNA appears to be adequate at the 0.3 mg/kg dose level and since this is clinically important and logically correlated directly with the SYN023 antibody administered the SYN023-002 study may be started despite the ongoing analysis of a RVNA-per-mg-SYN023 value that might be important in the SYN023-002 analysis.

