**Table 2.2-1 Treatment Allocation**

Treatment Allocation	Number of subjects
RVi + RIG	40
RVa + RIG	40
RVi + SYN023 0.3 mg/kg	40
RVa + SYN023 0.3 mg/kg	40
Total	160

The RVi and RVa regimens for post exposure prophylaxis are both five dose regimens. The initial dose of RVi and RVa will be co-administered with Study Drug (either RIG or 0.3 mg/kg SYN023) on Study Day 0. Rabies virus neutralizing activity (RVNA) and blood levels of SYN023 will be measured for the remainder of the trial while the rest of the post-exposure RVi and RVa doses are given. It is anticipated that RVNA will remain high during RVi and RVa administration and through the end of the study at Study Day 112. Pharmacodynamic efficacy will be defined as RVNA measured above 0.5 IU/mL with RVi and RVa for the duration of the trial and no more than 10% lower for SYN023 compared to RIG at any time point through Study Day 35. SYN023 concentrations and anti-SYN023 antibodies will also be measured.

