3.4 Subject Withdrawal and Replacement

Subjects were advised that they were free to withdraw from the study at any time. Over the course of the study, the Sponsor and Investigator or a delegate had the right to withdraw any subject from the study for one of the reasons described below; subject withdrawal will be done in accordance with inVentiv's SOP:

- Safety reason;
- non-compliance with protocol requirements;
- significant protocol deviation;

Subjects who withdraw or are withdrawn from the study after dosing will not be systematically replaced. Subjects who fail to complete the study through Study Day 28 may be replaced at the discretion of the sponsor.

4. Changes From the Protocol

For efficacy/PD analyses, AUC_{0-last} was replaced by $AUEC_{0-t}$, $AUC_{14-last}$ was replaced by $AUEC_{14-t}$, C_{max} was replaced by E_{max} , and T_{max} was replaced by $T_{max,E}$. This is standard nomenclature for such efficacy/PD parameters.

AUC_{0-inf} was removed from Efficacy/PD analyses because elimination phase cannot be calculated for rabies virus neutralizing activity (RVNA).

5. Primary and Secondary Parameters

The primary parameters will be $AUEC_{0-t}$ calculated on RVNA measured above 0.5 IU/mL. All other PD parameters will be regarded as secondary parameters (refer to Sections 10).

The safety, immunology and PK parameters will be regarded as secondary (refer to Sections 9, 11, and 12).

6. Analysis Populations

The analysis of safety and tolerability parameters will be based on the safety population detailed in Section 6.1 below. The analysis of immunogenicity (anti-SYN023 antibodies), PK, and PD parameters will be based on the Per-Protocol population detailed in Section 6.2 below.

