10.3 Efficacy/Pharmacodynamic Parameters

A total of 10 blood samples will be drawn from each subject for efficacy/PD analyses. Blood samples will be collected on Day 0, Day 1, Day 3, Day 7, Day 14, Day 28, Day 35, Day 42, Day 84, and Day 112.

RVNA will be used to calculate the following parameters by standard non-compartmental methods:

AUEC_{0-t}: area under the effect-time curve above the minimum rabies virus neutralizing activity threshold (0.5 IU/mL) from time 0 to the last measurable concentration, calculated using the linear trapezoidal method. Unit will be Day*IU/mL.

AUEC₀₋₇: area under the effect-time curve above the minimum rabies virus neutralizing activity threshold (0.5 IU/mL) from time 0 to 7 days, calculated using the linear trapezoidal method. In case where the 7 days RVNA value is missing, AUEC₀₋₇ will be interpolated at the discretion of the pharmacokineticist. Unit will be Day*IU/mL.

- AUEC₀₋₁₄: area under the effect-time curve above the minimum rabies virus neutralizing activity threshold (0.5 IU/mL) from time 0 to 14 days, calculated using the linear trapezoidal method. In case where the 14 days RVNA value is missing, AUEC₀₋₁₄ will be interpolated at the discretion of the pharmacokineticist. Unit will be Day*IU/mL.
- AUEC_{14-t}: area under the effect-time curve above the minimum rabies virus neutralizing activity threshold (0.5 IU/mL) from time 14 days to the last measurable concentration, calculated using the linear trapezoidal method. In case where the 14 days RVNA value is missing, AUEC_{14-t} will be interpolated at the discretion of the pharmacokineticist. Unit will be Day*IU/mL.
- AUEC₁₄₋₃₅: area under the effect-time curve above the minimum rabies virus neutralizing activity threshold (0.5 IU/mL) from time 14 days to 35 days, calculated using the linear trapezoidal method. In case where the 14 days or 35 days RVNA value is missing, AUEC₁₄₋₃₅ will be interpolated at the discretion of the pharmacokineticist. Unit will be Day*IU/mL.
- E_{max}: maximum observed effect. Unit will be IU/mL.
- T_{max,E}: time of observed E_{max}. Unit will be Day.

Some efficacy/PD parameters may not be calculated for all or some subjects, at the discretion of the inVentiv pharmacokineticist, if the concentration data is not deemed to be amenable to evaluation. Explanations for efficacy/PD parameters that could not be estimated will be provided in the CSR.

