10.4 Statistical Analyses

Individual and mean RVNA versus time curves will be presented using linear and semi-log scales for RVNA. Listings and descriptive statistics (number of observations, arithmetic mean, SD, coefficient of variation [CV%], median, Min, Max, geometric mean, and the percentage of subjects with RVNA values above 0.5 IU/mL [% > 0.5 IU/mL]) of the RVNA versus time as well as all PD parameters will be provided for each treatment.

For inferential analyses, data will be analysed as a two-factor factorial design. The two factors will be Vaccine including 2 levels (RVi and RVa) and Conmed including 2 levels (RIG and SYN023) as described in Table 10-1.

Table10-1: Two-factor factorial design with Vaccine and Immune Globulin (IG) as factors

		IG	
		RIG	SYN023
Vaccine	RVi	N _A =40	N _C =40
	RVa	N _B =40	N _D =40

Where N_X is the number of subjects planned to be dosed for Treatment X (X=A, B, C, D).

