10.4.1 Similarity Acceptance

Using GLM procedures in SAS[®], ANOVA will be performed on untransformed $T_{\max,E}$ and ln-transformed $AUEC_{0-t}$, $AUEC_{0-7}$, $AUEC_{0-14}$, $AUEC_{14-t}$, $AUEC_{14-35}$, and E_{\max} at the alpha level of 0.05. Factors incorporated in the model will include: Vaccine, IG, and Vaccine*IG. Vaccine, IG, and Vaccine*IG will be tested against the residual mean square error. In the case of a non-statistically significant Vaccine*IG interaction term, the analysis will be rerun excluding this term from the ANOVA model in order to obtain ratios and confidence intervals where appropriate. In the case of statistically significant Vaccine*IG interaction term, the analysis will be rerun for each vaccine separately. All sums of squares (Types I, II, III and IV) will be reported. Probability (p) values will be derived from Type III sums of squares. Coefficients of variation (CV%) will be estimated.

Based on pairwise comparisons of the ln-transformed $AUEC_{0-t}$, $AUEC_{14-t}$, and E_{\max} data, the ratio (RIG/SYN023) of the geometric least-squares means, calculated according to the formula “ $e^{(X-Y)} * 100$ ”, as well as the corresponding 90% geometric confidence intervals will be determined.

For $AUEC_{14-t}$, a statistically significant Vaccine*Conmed interaction term will be interpreted as a possible interference of RIG or SYN023 on the vaccines. In this case, each vaccine will be investigated separately.

Additional analyses may be performed.

Criteria for Similarity

Considering PP population, the 90% geometric confidence intervals of the ratio (RIG/SYN023) of least-squares means from the ANOVA of the ln-transformed $AUEC_{0-t}$ must be within 80.00% to 125.00%.

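### Meeting the SAP's only similarity criterion, on AUEC0-t, says almost nothing about the first week, and the protocol's early RVNA standard was left out of the SAP without being declared

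*SAP*

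**What the plan says.** **SAP.** Section 5 makes AUEC0-t the primary parameter, "calculated on RVNA measured above 0.5 IU/mL". Section 10.3 integrates it "from time 0 to the last measurable concentration, calculated using the linear trapezoidal method"; the last scheduled sample is Day 112. Section 10.4.1 then gives the only acceptance rule in the SAP: "Considering PP population, the 90% geometric confidence intervals of the ratio (RIG/SYN023) of least-squares means from the ANOVA" of log AUEC0-t "must be within 80.00% to 125.00"%.

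AUEC0-7 and AUEC0-14 are defined in 10.3 and go through the ANOVA in 10.4.1. The sentence that calls for RIG/SYN023 ratios and 90% intervals, however, names only AUEC0-t, AUEC14-t and Emax. Section 10.4.2 gives RIG/SYN023 ratios with 90% and 95% intervals at each sampling day from Day 1, without limits. Section 10.4 lists "the percentage of subjects with RVNA values above 0.5 IU/mL" among the descriptive statistics for each treatment, with no comparison between products.

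**Protocol.** Section 1.1 says that "on Day 7 post vaccination most individuals lack adequate rabies virus neutralizing activity", and section 1.5 treats Days 0-7 as an interval when vaccine-induced RVNA is unlikely. Section 1.6 states: "The goal of RIG and SYN023 is to rapidly establish protective rabies virus neutralizing levels in the rabies exposed person". Section 2.2 sets the standard: "Pharmacodynamic efficacy will be defined as RVNA measured above 0.5 IU/mL with RVi and RVa for the duration of the trial". The same sentence, repeated in 7.3, goes on to require that SYN023 be at most 10% lower than RIG at every time point up to Day 35.

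SAP section 4, which lists changes from the protocol, covers the renaming of PD parameters and the removal of AUC0-inf. It does not mention this definition.

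**The concern.** Passive antibody is given to cover the days before the vaccine works. Both products are followed by the same five-dose vaccine schedule, so most of a 112-day area reflects the vaccine response and little of it the passive product. Time spent below 0.5 IU/mL adds nothing to the area and carries no penalty.

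A conclusion of similarity to RIG under SAP 10.4.1 could therefore be read as covering the bridging period when the criterion is almost blind to it. The protocol has a standard that would cover that period. The SAP does not apply it, and a reader of SAP section 4 would not learn that it had gone.

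**Working it through.** The documents give no figure for the early share of AUEC0-t. The nearest stated figure is the power of 0.838 in protocol 7.7. It reproduces as 0.8376 (n = 40 per group, SD 3, difference 2, two-sided 0.05). It concerns a 10% margin on RVNA at a time point, not the 80-125% rule, so it does not bear on the size of this point.

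**Inputs**
- Early passive profile: Phase 1 means at 0.3 mg/kg from protocol Table 1.5-1, namely 0, 2.70, 3.68 and 4.44 IU/mL on Days 0, 1, 3 and 7. RIG's early RVNA is not in the documents, so this profile stands for whichever product is active early.
- RVNA over Days 14-112: flat at V = 5, 10 or 20 IU/mL. Only 20 has a source (protocol 7.7); 5 and 10 are assumptions.
- CV 25%: the top of the 15-25% range for RVNA in protocol 7.7. The AUC power statement there uses 10-20%.
- n: 80 vs 80 with vaccines pooled, or 40 vs 40 within a vaccine if the interaction is significant.

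**Step 1. Area above 0.5 IU/mL, Days 0-7** (linear trapezoid, floored at zero)
- Days 0-1: RVNA crosses 0.5 at 0.5/2.70 = 0.185 day; area = ½ × 0.815 × 2.20 = 0.90
- Days 1-3: (2.20 + 3.18)/2 × 2 = 5.38
- Days 3-7: (3.18 + 3.94)/2 × 4 = 14.24
- Sum: 20.5 Day*IU/mL

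**Step 2. Total and early share.** Days 7-14 = 3.5 × (3.94 + V − 0.5); Days 14-112 = 98 × (V − 0.5).

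| V | Days 7-14 | Days 14-112 | Total | Days 0-7 share |
|---|---|---|---|---|
| 5 | 29.5 | 441 | 491.1 | 4.2% |
| 10 | 47.0 | 931 | 998.6 | 2.1% |
| 20 | 82.0 | 1911 | 2013.6 | 1.0% |

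**Step 3. One product with zero RVNA on Days 1, 3 and 7, and the same V from Day 14.** Days 0-7 contribute nothing. Days 7-14 rise from 0 to V, so the area is 3.5 × (V − 0.5)²/V.
- V = 5: 14.2 + 441 = 455.2; ratio 491.1/455.2 = 1.079
- V = 10: 31.6 + 931 = 962.6; ratio 998.6/962.6 = 1.037
- V = 20: 66.5 + 1911 = 1977.5; ratio 2013.6/1977.5 = 1.018

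**Step 4. The criterion is an interval, so add its width.** The 90% limit factor is exp[t(0.95) × √ln(1 + CV²) × √(2/n)]. At CV 25% this is 1.067 for n = 80 per product and 1.096 for n = 40.
- 1.079 × 1.067 = 1.15
- 1.079 × 1.096 = 1.18

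Both are below 1.25. The lower limits, 1.079/1.067 = 1.01 and 1.079/1.096 = 0.98, are above 0.80. The criterion is met. At a ratio of 1.079 the observed interval stays inside the limits until CV exceeds about 61% (80 vs 80) or 41% (40 vs 40).

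**Step 5. A partial shortfall.** Halving RVNA on Days 1, 3 and 7 leaves AUEC0-t at 96.0% (V = 5) or 99.0% (V = 20) of its value. AUEC0-7 falls to about 42%, a ratio of about 239%. Each of those days would be 50% lower, well beyond the protocol's 10%.

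**Sensitivity.** At V = 50 the early share is 0.4%. In a weak-response profile with total area 368.6 it is 20.5/368.6 = 5.6%, and zero early RVNA leaves 90.3% of the area. That is a ratio of 1.107 and an upper limit of 1.107 × 1.096 = 1.21, which still passes. The share reaches about 16.5% only if the vaccine adds nothing, contrary to the protocol's expectation that RVNA stays high to Day 112.

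**The case against.** The strongest defence is that AUEC0-t fits the stated question. The primary objective is RVNA induced by the vaccines, the rationale is whether SYN023 inhibits that response, and protocol 3.6.1 says this is not an efficacy trial. That stands: the documents do not support calling AUEC0-t the wrong primary parameter. The point is what a pass on it may be taken to mean.

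Three stronger readings are tempting and also fail.

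- A reader might infer that the plan has no early criterion at all. Protocol 2.2 and 7.3 contain one, and a product that failed to bridge would fail both of its halves. The gap is in the SAP.
- A reader might infer that an early shortfall would go unseen. SAP 10.4.2 reports RIG/SYN023 ratios with intervals at Days 1, 3, 7 and 14, AUEC0-7 and AUEC0-14 are tested in the ANOVA, and the percentage above 0.5 IU/mL is tabulated. A shortfall would be visible but would not affect the declared conclusion. The safeguard also has a weakness: SAP 10.1 sets values below quantitation to zero, the early analyses use logs, and no rule is given for the log of zero. Subjects with no early activity could drop out of those ratios.
- A reader might infer that SYN023 is likely to fail early. Protocol 1.5 reports that all Phase 1 volunteers at 0.3 mg/kg exceeded 0.5 IU/mL for at least 35 days. The zero-activity case only tests what the criterion can detect.

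The early window should also not be called pre-vaccine: dose 1 is given on Day 0. It precedes the expected vaccine-induced response.

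**Conclusion.** The point holds as a mismatch between the SAP and the protocol, and as a limit on what AUEC0-t can support. With Days 14-112 at 5-20 IU/mL, the first week is about 1-4% of the area. Total loss of RVNA on Days 1, 3 and 7 moves the ratio to about 1.02-1.08, and in the least favourable of these cases at CV 25% the upper limit is 1.15 or 1.18, so similarity would still be declared.

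This rests on an assumed post-vaccine level (only 20 is documented), on Phase 1 SYN023 means from five subjects standing in for RIG's unstated early level, and on equal RVNA in both products from Day 14. The omission of the 10% standard, and its absence from SAP section 4, rest on no assumption. The change should be made, but the primary analysis need not be replaced.

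**What to change.** 1. Reconcile the SAP with protocol 2.2 and 7.3. Either apply the protocol definition to the Day 1-35 comparisons in SAP 10.4.2, saying whether the 10% refers to the point estimate or a confidence limit, or declare and justify its removal in SAP section 4.
2. Add AUEC0-7 and AUEC0-14 to the sentence in SAP 10.4.1 that calls for RIG/SYN023 ratios and 90% intervals. State a rule for zero values before log transformation, and use the same rule in 10.4.2.
3. At Days 1, 3, 7 and 14, report the SYN023 minus RIG difference, with 90% interval, in the proportion with RVNA of at least 0.5 IU/mL. This keeps subjects with zero values. Settle the boundary too: the SAP abbreviation list uses at least 0.5, while 10.4 uses above 0.5.
4. State in 10.4.1 that meeting the AUEC0-t criterion alone supports similar total RVNA over 112 days, not similar early (bridging) activity.

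All samples are already scheduled and both early areas already defined, so the cost is SAP wording, a few tables and a narrower similarity claim. If the 10% rule is applied as a formal confidence-limit test, it is demanding: at 40 per group, mean 20 and margin 2, power at one-sided 0.05 runs from 0.22 to 0.90 over CV 15-25% and a true deficit of 0-1 IU/mL. The sponsor should weigh that openly when choosing between the two options in item 1.

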### Criteria for Pharmacodynamic Similarity Acceptance

Rabies Virus Neutralizing Activity plotted against time will be created. Pharmacodynamic parameters for SYN023 mAb will be estimated using non-compartmental analysis. Cmax, Tmax, AUC0-last, AUC0-inf will be calculated. For the comparison of RIG to SYN023 with RVi and RVa vaccines: The 90% confidence intervals for the ratio of geometric means (RIG/SYN023) must be 80% to 125%. An ANOVA of the ln-transformed AUC0-inf will be run to determine the 90% confidence interval on the difference between treatments. The confidence interval limits derived on the log scale will be back-transformed to the raw AUC scale for comparison to the acceptance criteria.

To investigate any interference of SYN023 to the immune response generated by the vaccine, a non-inferiority test of the AUC14-last between RIG and SYN023 for each vaccine can be performed. The one-sided 90% confidence interval derived on the log transformed AUC from an ANOVA would be compared to the lower acceptance criterion of 80%.

Additionally, a non-inferiority test of the level of RVNA between RIG and SYN023 for each vaccine at selected time points, such as 14 or 28 days, can be performed using a Wilcoxon rank sum approach with a non-inferiority of 10% of the level associated with RIG. Pharmacodynamic efficacy will be defined as RVNA measured above 0.5 IU/mL with RVi and RVa for the duration of the trial and no more than 10% lower for SYN023 compared to RIG at any time point through Study Day 35.

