### **7.7 Sample Size Considerations**

The sample size for this Phase 2 study was selected based on requirement to consider noninferiority of the efficacy parameter, RVNA. The power analysis was performed in SAS 9.2 using the power procedure for noninferiority testing under the assumption of the sample size of 40 per group and likely margin corresponding to SYN023 being no less than 10% lower than RIG. Based on earlier studies, the mean RVNA for 0.3 mg/kg SYN023 of 20 with CV of 15-25% are reasonable. For assumed underlying differences of 0 to 1 IU/mL, there is over 80% to conclude non-inferiority of RVNA level at a specified time point. The sample size of 40 per treatment group should be sufficient to address the efficacy objectives of the study.

The assumptions that a difference of 2 or less is considered unimportant (the approximate mean value for 0.3mg/kg SYN023 of 20 was used), with the range in mean difference from -1 to 1, standard deviation of 3 and power of 0.8, the required sample size of 29 is needed to declare that the new treatment (SYN023) is not more tolerably inferior to the previous treatment (RIG). Also, the power analysis was performed for the sample size of 40, standard deviation 3 and the mean difference of 2. This resulted in the power of 0.838. The above results from the sample size and power analysis showed that the sample size of 40 should be sufficiently powered for this study.

Also, a power analysis for non-inferiority of the AUCs was performed using “PowerTOST”, an R CRAN package run under Rstudio version 0.99.491. Under the assumption of a lower non-inferiority bound of 0.9 (corresponding to SYN023 being no less than 10% lower than RIG), the selected sample size of 40 per group would provide over 80% power assuming a CV of 10-20%.

If no SAEs are observed among subjects in each dose group and the 40 subjects in the 3 dose groups combined, the one-sided exact upper 95% confidence bounds on the rate of SAE occurrence will be 45% and 18%, respectively.

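### The trial is sized for non-inferiority at a 10% margin, but the primary AUEC0-t has only a two-sided 80-125% rule, which a sufficiently higher SYN023 arm can fail

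*SAP*

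**What the plan says.** **Sizing.** Protocol 7.7 states: "The sample size for this Phase 2 study was selected based on requirement to consider noninferiority of the efficacy parameter, RVNA". It gives a 10% margin, takes the view that "a difference of 2 or less is considered unimportant" around a mean of about 20 IU/mL, and reports two figures: "standard deviation of 3 and power of 0.8, the required sample size of 29 is needed" and, for 40 per group, "This resulted in the power of 0.838". For AUCs it uses a lower non-inferiority bound of 0.9 and claims over 80% power at CVs of 10-20%.

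**Efficacy definition.** Protocol 2.2 and 7.3 define pharmacodynamic efficacy in one direction only. Besides the 0.5 IU/mL threshold, SYN023 may not be more than 10% below RIG at any time point through Day 35.

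**Protocol criterion.** Protocol 7.3 sets a two-sided rule: "The 90% confidence intervals for the ratio of geometric means (RIG/SYN023) must be 80% to 125" per cent, applied to AUC0-inf. It adds two non-inferiority tests, both worded as optional: AUC14-last for each vaccine against 80%, and RVNA at selected days by a Wilcoxon approach with a 10% margin.

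**SAP.** Section 5 makes AUEC0-t primary. Section 10.4.1 gives it one criterion: "the 90% geometric confidence intervals of the ratio (RIG/SYN023) of least-squares means from the ANOVA" must fall within 80.00-125.00%. AUEC14-t gets a ratio and interval without a margin, and interference is read from the vaccine-by-immune-globulin interaction. Section 10.4.2 gives 90% and 95% intervals at nine days, again without a margin. Section 4 lists the renamed parameters and the removal of AUC0-inf. It does not mention the non-inferiority tests.

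**The concern.** The hypothesis that justified 40 per group is one-sided, whereas the rule that decides the primary endpoint is two-sided. A RIG/SYN023 interval that reaches below 80% means that SYN023 may be giving more RVNA than RIG, yet it fails the rule just as a loss would. The SAP then has no pre-specified statement that SYN023 met the requirement for which the trial was sized. A non-inferiority claim chosen after the data are seen would be post hoc, and its margin would be open to dispute because the protocol uses both 80% and 90% for different quantities.

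The direction is not fanciful. Measured RVNA includes the passive activity of SYN023, and protocol 1.5 itself discusses estimating that share.

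**Working it through.** **1. The plan's own figures are non-inferiority figures.** Inputs from protocol 7.7: margin 2, SD 3, true difference 0. Power is taken from the noncentral t with noncentrality 2 / (3 × √(2/n)).
- n = 29, one-sided 0.05: power 0.806 (0.793 at n = 28), so 29 is reproduced.
- n = 40, one-sided 0.025: power 0.838, as stated.

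Both are one-directional. No calculation in the documents covers an 80-125% rule.

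**2. The rule in numbers.** Assume a CV of 20% for AUEC0-t, the top of the protocol's AUC range.
- Log-scale SD: s = √ln(1 + 0.20²) = 0.198.
- Vaccines pooled, 80 per arm: SE = 0.198 × √(2/80) = 0.0313; t(157) = 1.655; half-width 0.0518.
- One vaccine, 40 per arm: SE = 0.0443; t(78) = 1.665; half-width 0.0737.

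The lowest observed RIG/SYN023 that passes is 0.80 × e^0.0518 = 0.843 pooled (SYN023/RIG 1.19), and 0.80 × e^0.0737 = 0.861 for one vaccine (SYN023/RIG 1.16).

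A 10% margin on SYN023/RIG is 1/0.90 = 111.1% on RIG/SYN023. For a true ratio θ below 1, approximately:
- P(80-125% rule passes) = Φ[(ln θ − ln 0.80 − half-width)/SE]
- P(non-inferior at 10%) = Φ[(ln 1.111 − half-width − ln θ)/SE]

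Example at θ = 0.85, pooled: (−0.1625 + 0.2231 − 0.0518)/0.0313 = 0.28, so 61%. Simulation agrees with these results:

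| True RIG/SYN023 | 80-125% rule, 80 per arm | Non-inferior at 10%, 80 per arm |
|---|---|---|
| 0.90 | 98% | about 100% |
| 0.85 | 61% | about 100% |
| 0.80 | 5% | about 100% |
| 0.75 | 0% | about 100% |

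With 40 per arm, the rule passes 39% at 0.85. If the CV were 40%, outside the protocol's range, the pooled rule would pass 26%, 5% and 0.3% at 0.85, 0.80 and 0.75, against 99.7-100% for non-inferiority at 10%.

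**3. Could the ratio be that low?** Protocol Table 1.5-1 gives mean RVNA after 0.3 mg/kg without vaccine. Linear trapezoids over Days 0-84 are 1.35 + 6.38 + 16.24 + 28.77 + 46.20 + 16.24 + 49.98 = 165.2 IU·day/mL. To turn this into a ratio, assume that vaccine RVNA is zero to Day 7, rises linearly to M at Day 14 and stays flat to Day 112, that passive RVNA adds to it, and that there is no interference. The RIG contribution is not in the documents, so it is varied as a share of SYN023's passive curve:

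| M (IU/mL) | RIG share 0% to 50% | RIG share 75% |
|---|---|---|
| 3 | 0.61 to 0.80 | 0.90 |
| 5 | 0.73 to 0.86 | 0.93 |
| 10 | 0.85 to 0.93 | 0.96 |
| 20 | 0.92 to 0.96 | 0.98 |

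At a 100% share the ratio is 1.00. At M = 20 the pooled rule passes at least 99.7% of the time at CV 20%.

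**4. Which one-sided limit?** With 80 per arm and CV 20%, suppose SYN023 is truly 10% lower (RIG/SYN023 = 1.111). An upper limit of 125% would call it non-inferior 98% of the time; a limit of 111.1% does so 5% of the time. At a true ratio of 1.15 the figures are 84% and 0.3%.

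**The case against.** Similarity was a deliberate choice. Protocol 7.3 puts the 80-125% rule under a similarity heading, the SAP keeps it, and the primary objective is to compare RVNA, not to show non-inferiority. The protocol also warns that high antibody levels may impair the vaccine response, so a higher total is not automatically a success. This stands as a reason to keep the 80-125% criterion. It does not explain why the hypothesis used for sizing has no test in the SAP.

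Four stronger readings are tempting, and the documents do not support them:
- **That a higher SYN023 arm would fail.** Failure depends on how much higher it is and on the CV. A SYN023 arm about 11% above RIG (ratio 0.90) still passes 98% of the time, pooled at CV 20%. The 5% at a ratio of 0.80 is simply the rule's error rate at its own boundary.
- **That no non-inferiority conclusion exists anywhere.** Protocol 7.3 offers two, on AUC14-last and on RVNA by day. They are optional, and the SAP specifies neither.
- **That the report could not tell higher from lower.** The ratios and intervals in SAP 10.4.1 and 10.4.2 show the direction. What is missing is a pre-specified conclusion.
- **That 125% is the natural non-inferiority limit.** It corresponds to a 20% margin, twice the 10% in protocol 2.2, 7.3 and 7.7. The 80% non-inferiority criterion in protocol 7.3 belongs to AUC14-last.

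**Conclusion.** The mismatch is real. The sample size rests on one-sided non-inferiority at 10%, the primary endpoint is judged only by a two-sided 80-125% rule, and the SAP omits the protocol's non-inferiority tests without saying so. At CV 20% the rule starts to fail once the observed SYN023/RIG exceeds about 1.19 with the vaccines pooled, or 1.16 for a single vaccine. It passes at most 5% of the time when SYN023 is truly 25% or more above RIG.

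How likely that is cannot be settled from the documents, because the RIG level, the vaccine RVNA and the CV of AUEC0-t are not given. Under the assumed curves the loss can be large when vaccine RVNA is about 10 IU/mL or less and RIG contributes little. It is small if the protocol's planning mean of 20 IU/mL describes the vaccine plateau. The correction is worth making because it is nearly free, but the trial should not be described as bound to fail.

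**What to change.** 1. In SAP 10.4.1, keep the 80.00-125.00% similarity criterion unchanged and add: SYN023 is non-inferior to RIG on AUEC0-t if the upper limit of the same 90% interval for RIG/SYN023 is at or below 111.1%, the 0.90 bound of protocol 7.7. Do not use 125% under the name non-inferiority. Mirror the sentence in protocol 7.3.
2. State how each outcome is reported. If only the 80% limit fails, report SYN023 as higher than RIG. If the upper limit lies between 111.1% and 125% and the lower limit holds, report similarity with non-inferiority at 10% not shown.
3. Carry the protocol 7.3 tests of AUC14-last (80%) and RVNA by day (10%) into the SAP with their margins, or list them in SAP 4 as dropped.
4. Settle this before anyone sees RVNA by treatment, including at the Day 42 review.

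**Cost.** A few sentences; the interval is already planned. No multiplicity adjustment is needed, because both upper-limit claims are nested and come from one interval. If the true ratio is 125% or more, either false claim needs an upper limit at or below 125%. Between 111.1% and 125%, only the non-inferiority claim can be false; at 80% or below, only similarity can be false. Each chance is at most 5%.

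**Downside.** The 10% bound is stricter. At a true ratio of 1 and CV 20%, power is Φ[(0.1054 − 0.0518)/0.0313] = 96% with 80 per arm, and Φ[(0.1054 − 0.0737)/0.0443] = 76% with 40 per arm if a significant interaction leads to separate analyses by vaccine.
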